5.2 Toxicities and Dosing Delays/Dose Modifications

Any patient who receives treatment on this protocol will be evaluable for toxicity. Dose modifications are not allowed during cycle 1, days 0-29, during DLT determination. Any dose modifications deemed necessary for patient safety during this period by the treating investigator would constitute a DLT for that patient – even if not meeting the explicit DLT definition as reported in Section 5.1.2. Each patient will be assessed for the development of toxicity according to the Time and Events Table (Section 6.2). Toxicity will be assessed according to the NCI Common Terminology Criteria for Adverse Events (CTCAE), version 5.0. Dose adjustments should be made according to the system showing the greatest degree of toxicity.

Table 2. Cabozantinib Dose Modifications	
Current Dose	Adjusted Dose
60 mg	40 mg
40 mg	20 mg

20 mg	Discontinue
-------	-------------

- 5.2.1** Dose re-escalation to previous dose may be considered at the discretion of the investigator for grade 2-3 AEs which have resolved or recovered to grade 1 (or baseline) and deemed tolerable and easily managed by optimized supportive treatment. All dose reductions for grade 4 AEs will be permanent unless otherwise noted.
- 5.2.2** If more than one toxicity occurs requiring dose reduction, the dose administered should be based on the most severe toxicity.
- 5.2.3** Treatment delay of more than 42 days from last intended therapy will result in treatment discontinuation unless there is unequivocal evidence that the subject is benefitting. In this situation, a subject may be able to restart therapy with a dose reduction upon resolution of the toxicity per the discretion of the investigator.
- 5.2.4** If a patient experiences neutropenic fever at any point in the treatment cycle, chemotherapy will be delayed until ANC \geq 1,000 and antibiotic treatment of the event is completed. When treatment resumes, consider one dose level reduction as per Table 2.
- 5.2.5** Dose will not be modified for cholangitis attributable to biliary obstruction/stent occlusion unless this occurs in the setting of \geq grade 3 neutropenia.
- 5.2.6** Laboratory abnormalities that are not directly attributable to treatment (i.e., hyperglycemia) or not clinically relevant (i.e., lymphopenia) do not require modification of dosing.

Table 3. Dose Modifications for Hematologic Toxicity	
Hematologic Toxicity	Dose Adjustment for Cabozantinib
ANC \geq 1000/mm ³ AND Platelets \geq 60,000/mm ³	Treat as scheduled
ANC 500-999/mm ³ OR Platelets 40-59,999/mm ³	Hold cabozantinib up to a maximum of 28 days until ANC \geq 1000/mm ³ AND platelets \geq 60,000/mm ³ then consider resuming at next lower dose level as detailed in Table 2. If not resolved, then discontinue treatment.
ANC < 500/mm ³ OR Platelets < 40,000/mm ³	Hold cabozantinib up to a maximum of 28 days until ANC \geq 1000/mm ³ AND platelets \geq 60,000/mm ³ then resume at next lower dose level as detailed in Table 2. If not resolved, then discontinue treatment.
Note: Laboratory abnormalities that are not directly attributable to treatment (i.e., basophilia), anemia, or not clinically relevant (i.e., lymphopenia) do not require dose modification. All dose adjustments for toxicity will be described in the clinical record.	

Table 4. Dose Modifications for Non-Hematologic Toxicity		
Non-Hematologic Toxicity	Criteria	Dose Adjustment for Cabozantinib
Alopecia	Any Grade	No modification to doses
Venous thromboembolism	Any Grade	Hold cabozantinib until anticoagulation has been established. No modification to doses. Low molecular weight heparins are the preferred management for thrombotic events; oral anticoagulants (e.g., warfarin or other coumarin-related agents, direct thrombin or direct FXa inhibitors, or antiplatelet agents, or chronic use of aspirin above low dose levels for cardioprotection per local applicable guidelines) are not allowed.
Arterial thromboembolism	Grade \geq 3	Discontinue cabozantinib
Visceral perforation or fistula formation	Any Grade	Discontinue cabozantinib
Reversible posterior leukoencephalopathy syndrome	Any Grade	Discontinue cabozantinib

Wound dehiscence	Any Grade	Hold cabozantinib until complete healing has taken place
Nausea and vomiting	Grade >3 (ongoing after maximal anti-emetic therapy)	Consider decrease or discontinuation of cabozantinib
Hyperbilirubinemia	Grade \geq 3	Hold cabozantinib up to a maximum of 42 days until toxicity resolves to Grade \leq 2, then consider resuming at same dose as before. If not resolved, then discontinue all treatment. Dose will not be modified for cholangitis attributable to biliary obstruction/stent occlusion unless this occurs in the setting of >grade 3 neutropenia
Diarrhea	Tolerable Grade 1-2	
 • Continue with study treatment and consider dose reduction • Initiate treatment with an antidiarrheal agent (e.g., loperamide 4 mg followed by 2 mg after each episode of diarrhea [maximum: 16 mg loperamide per day]) • Dietary modifications (e.g., small lactose-free meals, bananas and rice) • Intake of isotonic fluids (1-1.5 L/day) • Re-assess after 24 hours: 
 ○ Diarrhea resolving to baseline bowel habits: gradually add solid foods and discontinue or decrease antidiarrheal treatment after 12 h diarrhea-free interval ○ Diarrhea not resolving: Continue/resume antidiarrheal treatment
	Intolerable Grade 2, Grade 2 > 48 h, or \geq Grade 3	
 • Interrupt study treatment • Ask subject to attend clinic • Rule out infection (e.g., stool sample for culture) 
 ○ Administer antibiotics as needed (e.g., if fever or Grade 3-4 neutropenia persists > 24 h) • Administer fluids (1-1.5 L/day orally or IV, as appropriate) for hydration or to correct electrolyte abnormalities • For Grade 3-4 or complicated lower grade diarrhea consider hospitalization and IV hydration • Re-assess after 24 h 
 ○ Diarrhea resolving to baseline bowel habits or Grade \leq 1: consider restarting study treatment at reduced dose 
Diarrhea not resolving: Start and or continue antidiarrheal treatment (e.g., loperamide 4 mg followed by 2 mg after each episode of diarrhea [maximum: 16 mg loperamide per day]). Consider starting second line antidiarrheal or referral to gastroenterologist

Hemorrhage	Serious and life-threatening bleeding events or recent hemoptysis (≥ 2.5 mL of red blood)	Cabozantinib should be discontinued.
Hypertension	> 150 mm Hg (systolic) and < 160 mm Hg OR > 100 mm Hg (diastolic) and < 110 mm Hg	
 Optimize antihypertensive medications by adding new or additional antihypertensive medications and/or increase dose of existing medications. Reduce cabozantinib treatment by one dose level if optimal antihypertensive therapy (usually to include 3 agents) does not result in BP <150 mm Hg systolic or <100 mm Hg diastolic If subject is symptomatic interrupt cabozantinib treatment
	≥ 160 mm Hg (systolic) OR ≥ 110 mm Hg (diastolic)	
 Reduce cabozantinib by one dose level or interrupt cabozantinib treatment per investigator discretion Add new or additional anti-hypertensive medications and/or increase dose of existing medications and monitor subject closely for hypotension. If optimized antihypertensive therapy (usually to include 3 agents) does not result in BP < 150 mm Hg systolic or < 100 mm Hg diastolic, cabozantinib treatment should be dose reduced further or interrupted Cabozantinib treatment should be dose interrupted if upper limits of systolic BP (≥ 160 mm Hg) are sustained and not adequately manageable or if systolic BP is > 180 mm Hg or diastolic BP > 110 mm Hg, or if subject is symptomatic Re-start cabozantinib treatment at the most tolerable dose and re-escalate only if BP falls to and is sustained at < 150 mm Hg systolic and < 100 mm Hg diastolic
	Hypertensive emergency	
 Discontinue cabozantinib treatment
Hand-Foot Syndrome	Grade 1	
 Cabozantinib treatment may be continued at the current dose if PPES is clinically insignificant and tolerable. Otherwise, cabozantinib should be reduced to the next lower dose level. Start urea 20% cream twice daily AND clobetasol 0.05% cream once daily. Reassess at least weekly; if PPES worsens at any time or does not improve after 2 weeks, proceed to the intervention guidelines for Grade 2.

	Grade 2	
 • Cabozantinib treatment may be continued if PPES is tolerated. Cabozantinib should be dose reduced or interrupted if PPES is intolerable. Continue urea 20% cream twice daily AND high potency steroid cream (e.g., clobetasol 0.05%) once daily and add analgesics (e.g., NSAIDs/gamma-aminobutyric acid agonists) for pain control if needed. Reassess at least weekly; if PPES worsens or affects self-care, proceed to the intervention guidelines for Grade 3.
	Grade 3	
 • Interrupt cabozantinib treatment until severity decreases to Grade 1 or 0. Continue treatment of skin reaction with high potency steroid cream (e.g., clobetasol 0.05%) twice daily AND analgesics. Resume study drug at a reduced dose if PPES recovers to Grade \leq 1. Discontinue subject from study treatment if PPES does not improve within 6 weeks.
Proteinuria	\leq 1 mg/mg (\leq 113.1 mg/mmol)	
 • No change in cabozantinib treatment or monitoring
	> 1 and < 3.5 mg/mg (> 113.1 and < 395.9 mg/mmol)	
 • Consider confirming with a 24-h protein assessment within 7 days • No change in cabozantinib treatment required if UPCR \leq 2 mg/mg or urine protein \leq 2 g/24 h on 24-h urine collection. • Dose reduce or interrupt cabozantinib treatment if UPCR > 2 mg/mg on repeat UPCR testing or urine protein > 2 g/24 h on 24-h urine collection. Continue cabozantinib on a reduced dose if UPCR decreases to < 2 mg/mg. Consider interrupting cabozantinib treatment if UPCR remains > 2 mg/mg despite a dose reduction until UPCR decreases to < 2 mg/mg. Restart cabozantinib treatment at a reduced dose after a dose interruption. • Repeat UPCR within 7 days and once per week. If UPCR < 1 mg/mg on 2 consecutive readings, UPCR monitoring can revert to protocol-specific times. (Second reading is confirmatory and can be done within 1 week of first reading.) If UPCR remains > 1 mg/mg and < 2 mg/mg for 1 month or is determined to be stable (< 20% change) for 1 month, check urine protein/creatinine per protocol or as clinically indicated.
	Nephrotic syndrome	
 • Discontinue cabozantinib treatment
Osteonecrosis (including jaw)	Grade 1-4	
 • Discontinue cabozantinib treatment

Other toxicity possibly attributable to study treatment	Intolerable Grade 2 that cannot be adequately managed	
 • Hold treatment or dose reduction at discretion of treating investigator. • Note: It is recommended that dose holds be as brief as possible.
	Grade 3	
 • Hold treatment and monitor toxicity every 1-2 weeks. If toxicity resolves to \leq Grade 1 (or baseline) within 6 weeks, treatment may be resumed with one dose level reduction. • Note: It is recommended that dose holds be as brief as possible.
	Grade 4	
 • Discontinue cabozantinib unless the following criteria are met: 
 ○ Subject is deriving clear clinical benefit as determined by the investigator ○ Toxicity can be managed with a dose reduction following recovery to Grade 1 (or baseline) and optimal medical care

Note: Laboratory abnormalities that are not directly attributable to treatment (i.e., hyperglycemia), or can be managed easily (e.g. hypokalemia), or are not clinically relevant do not require dose modification. All dose adjustments for toxicity will be described in the clinical record.
		

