5.1.2 Dose Limiting Toxicities

A DLT will be any of the following occurring during the first 29 days of therapy, attributed (possibly, probably, or definitely) to the drug following day 1 treatment as assessed per the NCI CTCAE v5.0.

1. Grade 4 or greater hematological toxicity with the exception of uncomplicated grade 4 leukopenia/ neutropenia lasting <7 days)
2. Grade 3 or higher thrombocytopenia with bleeding
3. Grade 3 or greater febrile neutropenia.
4. Grade 3 or greater non-hematological toxicity, except nausea, vomiting, diarrhea (exception only when lasting <3 days, or without supportive care measures, such as anti-diarrheal medications), hyperbilirubinemia (secondary to biliary obstruction), alopecia, fatigue, and hypersensitivity reaction
5. Any death not clearly due to the underlying disease or extraneous causes.
6. Grade 3 or higher electrolyte abnormality that lasts >72 hours, or is clinically complicated, or does not resolve spontaneously or with conventional medical interventions.

Any dose modifications deemed necessary for patient safety during this period by the treating investigator would constitute a DLT for that patient – even if not meeting the explicit DLT definition as reported in Section 5.1.2. With completion of cycle 1, and following DLT determination (**yes vs. no**) on cycle 2 day 1, cycle 2 may begin.

Information on dose limiting toxicity events must be entered within one business day, recorded locally and entered into Case Report Forms (CRFs) on the web-based electronic data capture (EDC) system of the University of Michigan.

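### Tables 3 and 4 order cycle 1 holds for events the DLT list exempts or omits, and the text is inconsistent on whether a hold is a dose modification and therefore a DLT

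*Combined protocol and SAP*

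**What the plan says.** Section 5.2 states: "Dose modifications are not allowed during cycle 1, days 0-29, during DLT determination". Its next sentence gives the consequence: "Any dose modifications deemed necessary for patient safety during this period by the treating investigator would constitute a DLT for that patient", even when the event is not on the explicit list. Section 5.1.2 repeats that sentence, which is called the catch-all below.

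The list in 5.1.2 has exemptions. Item 1 counts "Grade 4 or greater hematological toxicity with the exception of uncomplicated grade 4 leukopenia/ neutropenia lasting <7 days". Item 2 counts grade 3 thrombocytopenia only with bleeding. Item 4 exempts, among others, diarrhea of under 3 days and fatigue. The yes/no call is made on cycle 2 day 1: "With completion of cycle 1, and following DLT determination" on that day, the next cycle may start.

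Tables 3 and 4 tell sites what to do when toxicity occurs and are not limited to later cycles. For ANC below 1000 or platelets below 60,000, Table 3 says "Hold cabozantinib up to a maximum of 28 days until ANC" and platelets recover. For ANC below 500 or platelets below 40,000 it adds "then resume at next lower dose level as detailed in Table 2". Table 4 orders interruptions for diarrhea and for other grade 3 toxicity.

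**The concern.** DLT yes/no is the primary endpoint (11.1). It sets the dose for each next patient (11.3) and the RP2D (11.4). When a table orders a hold in cycle 1 for an exempt event, the site must decide whether that hold is a dose modification under the catch-all. If it is, the exemption has no effect. If it is not, a patient can miss much of the 29-day window and still count as free of DLT. The protocol does not say which is meant, and up to four sites will be deciding.

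**Working it through.** **Step 1. Events that the list spares and the tables hold.**

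| Cycle 1 event | DLT list (5.1.2) | Action in Tables 3-4 | After the hold |
|---|---|---|---|
| ANC below 500, uncomplicated, under 7 days | Exempt (item 1) | Hold, up to 28 days | Resume one level lower |
| ANC 500-999, uncomplicated, under 7 days | Exempt or not listed | Hold, up to 28 days | Consider one level lower |
| Platelets 40-59,999, no bleeding | Not listed | Hold, up to 28 days | Consider one level lower |
| Grade 3 diarrhea, under 3 days | Exempt (item 4) | Interrupt | Consider a reduced dose |
| Grade 2 diarrhea, over 48 h | Below the item 4 grade | Interrupt | Consider a reduced dose |
| Grade 3 fatigue (no row of its own, so the other-toxicity row) | Exempt (item 4) | Hold | May resume one level lower |

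The ANC rows need no CTCAE cut-off: short uncomplicated grade 4 is exempt and lower grades are not listed. The platelet row assumes that 40-59,999 is below grade 4, since the protocol prints no cut-offs.

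**Step 2. Is a hold a modification?**

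- Pointing to yes: Tables 3 and 4 are titled as dose modifications and their main action is a hold. The hyperbilirubinemia row offers hold, resumption at the same dose or discontinuation, with no reduction, yet words its cholangitis exception as the dose not being modified.
- Pointing to no: the section heading, "Toxicities and Dosing Delays/Dose Modifications", names delays apart from modifications. "Table 2. Cabozantinib Dose Modifications" lists only reductions and discontinuation. The venous thromboembolism row orders a hold and says in the same cell that doses are not modified.

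**Step 3. Later reductions do not settle the score.** The catch-all covers only the cycle 1 period. A Table 3 hold begun on the day 15 blood count may run to day 15 + 28 = day 43, so the reduction that follows can fall after the day 29 call. In the rows that say to consider a lower dose, resuming at the same dose is allowed.

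**Step 4. Effect on the correct dose, without a model.** The plan gives no figure to reproduce here. Let p be a Table 7 DLT rate that excludes holds, and h the assumed share of patients without a listed DLT who have a counted hold, equal at each dose. The rate with holds counted is q = p + (1 - p)h, which reaches 0.35 at h = (0.35 - p)/(1 - p).

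- Scenario 1, 60 mg, p = 0.35: h = 0. At h = 0.01, q = 0.35 + 0.65 × 0.01 = 0.3565, and the correct dose becomes 40 mg. The 40 mg rate (p = 0.27) stays within the limit up to h = 0.08/0.73 = 0.110.
- Scenario 2, 40 mg, p = 0.35: h = 0, so any counted hold moves the correct dose to 20 mg.
- Scenario 3, 60 mg, p = 0.30: h = 0.05/0.70 = 0.071. At h = 0.05, q = 0.335; at h = 0.10, q = 0.370.

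If Table 7 already includes holds, leaving them out changes nothing in Scenarios 1 and 3. In Scenario 2 it makes 60 mg acceptable only if h is at least (0.50 - 0.35)/0.65 = 0.231.

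**Step 5. Effect on a single trial, illustrative.** The protocol states no prior, so assume a power model p_i = s_i^exp(a) with s = 0.20, 0.27, 0.35, a ~ N(0, v), v = 0.5, 1.34 or 2, and full follow-up. Ranges cover the three variances and both plug-in and posterior-mean estimates. The splits of 32 patients and the DLT counts are assumed; the 16 and 22 at 60 mg borrow Table 7's expected numbers at the MTD.

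| Patients at 40 / 60 mg | DLTs at 40 / 60 mg | 60 mg estimate | RP2D |
|---|---|---|---|
| 16 / 16 | 4 / 5 | 0.328-0.330 | 60 mg |
| 16 / 16 | 4 / 6 | 0.357-0.358 | 40 mg |
| 16 / 16 | 5 / 5 | 0.360-0.362 | 40 mg |
| 10 / 22 | 2 / 6 | 0.281-0.287 | 60 mg |
| 10 / 22 | 2 / 7 | 0.312-0.315 | 60 mg |
| 10 / 22 | 2 / 8 | 0.343 | 60 mg |
| 10 / 22 | 2 / 9 | 0.371-0.373 | 40 mg |

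Rescoring one held patient changes the dose in the first split. In the second it takes two from 7 DLTs, or three from 6.

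**The case against.** A reader might infer that the cycle 1 rules cannot all be followed. The documents do not support that. The catch-all follows the ban directly and says how a necessary modification is scored, so a site can hold as the tables direct, record a DLT and comply with everything. The override of the list is deliberate.

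It can also be argued that a hold is plainly a modification, given the table titles and the hyperbilirubinemia row, and that the thromboembolism row may mean only that the dose level is unchanged on resumption. That is a fair reading, but it leaves the heading and Table 2 unexplained, and it voids exemptions that someone chose to write.

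Two extensions are tempting and weak. Grade 3 hyperbilirubinemia from biliary obstruction is not a clear clash: 5.2.6 and the Table 4 note spare laboratory changes not attributable to treatment, and the row has a cholangitis exception. Nor does the ambiguity clearly reach adverse event recording: 8.1 speaks of protocol treatment being modified, not the dose, and an interruption falls naturally under that.

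On size, the examples sit near the limit. Table 7 places two rates exactly at 35%, and its expected 16 patients is an average over simulated trials, 17% of which stop early. With 4 DLTs at 60 mg in the first split, one more changes nothing; with 6, 40 mg is chosen before any hold is counted. Section 9.1.9 does not list neutropenia among the common, grade 3-4 or early-onset events, though it lists diarrhea and thrombocytopenia. These points stand. Central dose assignment, monthly data review and source verification reduce divergence between sites, but none of them defines the term.

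**Conclusion.** The point holds as an inconsistency in the rules that define the primary endpoint. For the six events in the first table, the same cycle 1 hold can be scored DLT or non-DLT depending on how a site reads one undefined term. If holds count, several listed exemptions have no effect; if they do not, nothing limits how much of the window a patient can miss and still be scored DLT-free.

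The size is not known. Hold frequency in 29 days is not in the documents, nor is whether the 20/27/35% expectations include holds. The arithmetic shows only that one to three rescored patients of 32 can change the RP2D when the estimate lies close to 35%. It rests on an assumed prior and assumed data and does not estimate how often this would happen. The text should be corrected, but the design need not change.

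**What to change.** In 5.2, state that Tables 3 and 4 apply from day 1, and that for the catch-all a dose modification means a hold, reduction or discontinuation in days 1-29, so that a hold in that window is a DLT. Delete or reword the exemptions in items 1 and 4 of 5.1.2 that this overrides.

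If the sponsor prefers to keep the exemptions, state instead that a table-directed hold for an exempt or unlisted event is not a DLT unless missed doses in days 1-29 exceed a stated number, or a reduction or discontinuation is decided by the cycle 2 day 1 call. Items 1 and 4 then still need aligning with the tables, because Table 3 requires a lower dose after ANC below 500 and Table 4 resumes one level lower after grade 3 fatigue. Reductions that begin after day 29 should not be counted: 5.1.2 fixes the call on that day and 11.3 treats observation as complete then.

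Under either option, confirm that the 20/27/35% expectations use the same definition. The cost is a few sentences and no new data collection; Table 7 needs re-running only if it used the other definition. Counting holds may lower the RP2D, while not counting them lets it rest partly on patients with missed doses.

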- 3.1.15 No known brain metastasis unless adequately treated with radiotherapy and/or surgery and stable for at least 4 weeks before registration. Eligible subjects must have been without corticosteroid treatment at the time of registration.
- 3.1.16 Must not have undergone a major surgery (e.g., GI surgery, removal or biopsy of brain metastasis) within 8 weeks before first dose of study treatment. Complete wound healing from major surgery must have occurred 1 month before first dose and from minor surgery (e.g., simple excision, tooth extraction) at least 10 days before first dose. Subjects with clinically relevant ongoing complications from prior surgery are not eligible.
- 3.1.17 Must not have an active second malignancy other than non-melanoma skin cancer or cervical carcinoma in situ. Patients with history of malignancy are eligible provided primary treatment of that cancer was completed > 1 year prior to enrollment and the patient is free of clinical or radiologic evidence of recurrent or progressive malignancy.
- 3.1.18 Must not have uncontrolled, significant intercurrent or recent illness including, but not limited to the following conditions:
- a. Cardiovascular disorders:
 - i. Congestive heart failure New York Heart Association Class 3 or 4, unstable angina pectoris, serious cardiac arrhythmias.
 - ii. Uncontrolled hypertension defined as sustained blood pressure (BP) > 150 mm Hg systolic or > 100 mm Hg diastolic despite optimal antihypertensive treatment.
 - iii. Stroke (including transient ischemic attack [TIA]), myocardial infarction (MI), or other ischemic event, or thromboembolic event (e.g., deep venous thrombosis, pulmonary embolism) within 6 months before first dose.
 - iv. Presence of known arterial aneurysm.
 - b. Gastrointestinal (GI) disorders including those associated with a high risk of perforation or fistula formation:
 - i. The subject has evidence of tumor invading the GI tract, active peptic ulcer disease, inflammatory bowel disease (e.g., Crohn's disease), diverticulitis, cholecystitis, symptomatic cholangitis or appendicitis, acute pancreatitis, acute obstruction of the pancreatic duct or common bile duct, or gastric outlet obstruction.
 - ii. Abdominal fistula, GI perforation, bowel obstruction, or intra-abdominal abscess within 6 months before first dose. Note: Complete healing of an intra-abdominal abscess must be confirmed before first dose.

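### Table 4 (Hypertension): the two failed-control bullets use a negated *or* where *and* fits the rest of the protocol, so the lower row, read literally, directs no dose reduction for an isolated raised component

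*Combined protocol and SAP*

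**What the plan says.** All of the dosing text is in Section 5.2, Table 4, under Hypertension.

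- **Lower row, entry:** "> 150 mm Hg (systolic) and < 160 mm Hg OR > 100 mm Hg (diastolic) and < 110 mm Hg". One raised component is enough.
- **Lower row, actions:** optimize antihypertensives; reduce by one level if optimal therapy (usually three agents) "does not result in BP <150 mm Hg systolic or <100 mm Hg diastolic"; and "If subject is symptomatic interrupt cabozantinib treatment".
- **Upper row, entry:** systolic of at least 160 or diastolic of at least 110, again on either component.
- **Upper row, first bullet:** "Reduce cabozantinib by one dose level or interrupt cabozantinib treatment per investigator discretion".
- **Upper row, failed control:** a further reduction or an interruption if optimized therapy "does not result in BP < 150 mm Hg systolic or < 100 mm Hg diastolic, cabozantinib treatment should be dose reduced" further or interrupted.
- **Upper row, restart:** "re-escalate only if BP falls to and is sustained at < 150 mm Hg systolic and < 100 mm Hg diastolic".

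Outside the table, Section 3.1.18 a.ii excludes patients with "Uncontrolled hypertension defined as sustained blood pressure (BP) > 150 mm Hg systolic or > 100 mm Hg diastolic despite optimal antihypertensive treatment".

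**The concern.** The failed-control bullet is the lower row's only directed dose reduction. The row admits a patient on one raised component, but a negated *or* makes the reduction depend on both staying raised. A patient who enters at 155/85 already has a diastolic value below 100. On the literal wording, failure of therapy to lower the systolic value could not trigger the step unless the diastolic value also rose to 100 or more.

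What is at stake is the clarity of a safety instruction. A site that left the dose unchanged at a persistent 155/85 would be following the literal text, although the protocol elsewhere treats such a pressure as not controlled. Hypertension is a foreseeable event here: Section 9.1.9 lists it among reactions seen in at least 20% of cabozantinib-treated patients in the phase 3 HCC trial, and among Grade 3-4 reactions in at least 5%.

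**Working it through.** The plan has no figure to reproduce. The check is one of logic, applied to the thresholds in Table 4 and Section 3.1.18 a.ii.

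**Step 1. The two readings.** Let S be systolic and D diastolic pressure on optimal therapy, in mm Hg.

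- Literal: not (S < 150 or D < 100), which equals S ≥ 150 **and** D ≥ 100.
- With *and*: not (S < 150 and D < 100), which equals S ≥ 150 **or** D ≥ 100.

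**Step 2. Test readings.**

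| BP | Row entered | Uncontrolled by the 3.1.18 a.ii limits, if sustained | Literal trigger | Trigger with *and* |
|---|---|---|---|---|
| 149/99 | none | no | no | no |
| 155/85 | lower | yes | **no** | **yes** |
| 140/105 | lower | yes | **no** | **yes** |
| 155/105 | lower | yes | yes | yes |
| 150/85 | none | no | no | yes |
| 165/85 | upper | yes | no | yes |

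**Step 3. Where the readings differ in the lower row.** Take whole-number pressures that meet the row's entry criterion (S from 151 to 159, or D from 101 to 109) and do not reach the upper row (S < 160 and D < 110). The trigger with *and* applies to every such pair. The literal trigger applies only where S ≥ 150 and D ≥ 100. The pairs that differ are therefore:

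- S 151-159 with D < 100; or
- D 101-109 with S < 150.

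All are isolated elevations. The row still directs optimization of antihypertensives for these patients, and interruption if they are symptomatic. The gap is the directed reduction in an asymptomatic patient whose therapy is already optimal.

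**Step 4. The upper row.** At 165/85 the literal failed-control trigger is also silent. The first bullet has already directed reduction or interruption, however, and a later bullet directs interruption if systolic pressure of 160 or more is sustained and not adequately manageable. Only the further step in the third bullet is affected, once pressure has fallen to an isolated value below 160 or 110.

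**Step 5. The boundary.** Exactly 150 or exactly 100 lies outside the lower row's entry criterion and outside 3.1.18 a.ii, since both use a strict inequality. Changing *or* to *and* alone would make the bullet apply at 150/85, as the table shows. That follows from the protocol's own control limit of below 150.

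**Step 6. Which reading fits.** Either-component entry in both rows, the *and* in the re-escalation bullet and the *or* in 3.1.18 a.ii all describe control as needing both limits. Table 3 in the same section has the matching form: treatment is held for low neutrophils or low platelets, and resumption requires both to recover.

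**The case against.** The strongest reply is that the row resolves its own ambiguity. Because it admits patients on one component, a reader will naturally pair each limit with the component that is raised and act if that limit is missed. The re-escalation bullet and 3.1.18 a.ii guide the reader the same way. This largely stands: most clinicians would probably read the bullet as intended, nothing forbids a discretionary reduction, and symptoms or a rise to 160 or 110 bring other instructions into play. It limits the severity, but it does not make the wording right.

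Two comparators have limits. The re-escalation condition sits only in the upper row, so it shows how the protocol describes control but does not govern lower-row patients. Section 3.1.18 a.ii is an eligibility definition and requires sustained pressure.

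A reader might also infer more than the documents support:

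- **An effect on DLT counts or the MTD.** Section 5.2 does not allow dose modifications in cycle 1, and it counts any that the investigator deems necessary for safety as a DLT. The test is the investigator's judgement, not the Table 4 trigger. No effect on the primary endpoint is shown.
- **A 28-day delay.** From cycle 2 the Section 6.2 calendar schedules vital signs only on day 1. That holds under either wording, and an unchanged 155/85 at the next visit would again fail the literal trigger. The interval does not measure this defect.
- **A dose effect of 33% or 50%.** The steps from 60 to 40 mg and from 40 to 20 mg are Table 2's general steps for any toxicity. They do not measure how much this wording matters.
- **Different handling across sites.** This is possible with up to four sites, but nothing in the documents shows it.

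**Conclusion.** The point holds as a minor correction to safety wording. Followed exactly, both failed-control bullets require both components to remain raised, which is inconsistent with how the same table and the eligibility criteria describe control. The practical gap is confined to the lower row: asymptomatic patients on optimal therapy with isolated systolic 151-159 (diastolic below 100) or isolated diastolic 101-109 (systolic below 150). The upper row is barely affected.

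The conclusion about the wording and its logic is firm. That *and* was intended is an inference from the surrounding text, though a strong one. The number of patients affected cannot be estimated, because Section 9.1.9 does not separate isolated from combined elevations. No effect on the primary endpoint, the sample size or any analysis is shown.

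**What to change.** In both failed-control bullets of Table 4 (Hypertension), replace *or* with *and* between the systolic and diastolic limits, so that therapy has failed unless systolic is below 150 and diastolic is below 100 mm Hg.

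Optionally, settle the boundary at the same time by rewording the condition as: *if systolic remains >150 or diastolic remains >100 mm Hg*. This matches the lower row's entry criterion and 3.1.18 a.ii, and it avoids directing a reduction at exactly 150 or 100.

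The cost is one word in each of two bullets, or one short clause in each with the optional version, at the next amendment. No new procedure, visit or data item is needed.
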